11 ADVERSE EVENTS

11.1 Safety Assessment Overview

Subjects will be evaluated every day while hospitalized. Subsequently, subjects will have 2 scheduled evaluations approximately 1 week after study enrollment and 1 month after discharge. At these follow-up visits, subjects and their parent(s) will be queried regarding recent medical events and/or procedures. Specific events will be documented to ascertain the nature and treatment of the event, including pain crises, episodes of acute chest syndrome, transfusions, and hospital admissions. These reportable events and diagnoses will be followed up by the nurse coordinator, who will review hospital charts, medical records, and office visit records for documentation in the follow-up visit forms in the case report form (CRF).

11.2 Adverse Events

An adverse event (AE) is defined for this study as any untoward medical occurrence in a subject or clinical investigation subject administered a pharmaceutical product that does not necessarily have a causal relationship with this treatment. An AE can therefore be any unfavorable and unintended sign (including an abnormal laboratory finding), symptom, or disease temporally associated with the use of a medicinal (investigational) product, whether or not related to the medicinal (investigational) product. AE data are recorded on the CRF.

Examples of an AE include:

- Exacerbation of a chronic or intermittent pre-existing condition including either an increase in frequency or intensity of the condition.
- Significant or unexpected worsening or exacerbation of the condition/indication under study.
- A new condition detected or diagnosed after study drug administration even though it may have been present prior to the start of the study.
- Signs, symptoms, or clinical sequelae of a suspected overdose of either study drug or a concurrent medication (“overdose” per se, should not be reported as an AE/SAE).
- Pre- or post-treatment events that occur as a result of protocol-mandated procedures (e.g., invasive protocol-defined procedures, modification of a subject’s previous drug treatment regimen).

An AE does **not** include

- Medical or surgical procedures (e.g., colonoscopy, biopsy). The medical condition that leads to the procedure is an AE.
- Social or convenience hospital admissions where an untoward medical occurrence did not occur.
- Day to day fluctuations of pre-existing disease or conditions present or detected at the start of the study that do not worsen.
- The disease/disorder being studied, or expected progression, signs, or symptoms of the disease/disorder being studied unless more severe than expected for the subject’s condition.

11.2.1 Adverse Events related to Increased Blood Pressure.

All site Principal Investigators are required to review blood pressure results at study enrollment, once daily during hospitalization, and at both follow-up clinic visits. The following blood pressure results must be reported as Adverse Events:

- A single blood pressure in which the systolic pressure is ≥ 140 mmHg ***and*** the diastolic pressure is ≥ 90 mmHg;
- a systolic pressure ≥ 140 mmHg on 2 more occasions in a rolling 24 hour period regardless of diastolic pressure;
- a diastolic pressure ≥ 90 mmHg on 2 more occasions in a rolling 24 hour period regardless of systolic pressure.

The AE form will allow commentary about suspected causes of the hypertension (e.g., crying or severe pain). Additionally, the Serious Adverse Event criteria will be reviewed to determine if any of the AE's related to increased blood pressure meet these definitions and will be reported accordingly.

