Criteria for Evaluation: Efficacy: Primary Endpoint: The duration of signs and symptoms of ACS or duration of hospitalization, whichever is less. The duration of signs and symptoms of ACS is defined as the interval between study entry and the time at which tachypnea, hypoxemia, increased work of breathing, and thoracic pain have resolved and supplemental oxygen and ventilatory support are no longer utilized. Secondary Endpoints: Clinical endpoints include: rating of pain, duration of hospitalization, supplemental oxygen, hypoxemia, and fever, number of transfusions, quantification of opioid use, rebound hospitalizations, pulmonary radiographic findings, and pulmonary function testing results. Laboratory endpoints include: VCAM ₁ , ICAM ₁ , P-selectin, L-selectin, vWF multimers, endothelial and monocyte microparticles, WBTF, NO, and sPLA ₂ . Safety: Adverse events (AEs), vital signs, physical examination, concomitant medications, complete blood count (CBC), urine output and daily fluid balance, blood culture, pulse oximetry, reticulocyte count, and baseline and interim history.
Study Design: Phase III randomized, double-blind, controlled clinical trial with two arms.
Study Population: Individuals of both genders 5 years of age and older with Hgb SS and Hgb Sβ ⁰ are eligible.
Major Inclusion Criteria: New episode of ACS; diagnosis of ACS within preceding 24 hours; and provision of informed consent.
Major Exclusion Criteria: Prior participation in this study; corticosteroids contraindicated for comorbid conditions; corticosteroid treatment in preceding 2 weeks.
Clinical and Laboratory Evaluations: The primary endpoint is the duration of signs and symptoms ACS (resolution of tachypnea, hypoxemia, increased work of breathing, and thoracic pain as well as the cessation of medical interventions to support respiration). Other clinical evaluations include subject pain, requirement for opioid analgesics, number of transfusions, use of supplemental oxygen, duration of hypoxemia, duration of hospitalization, and duration of fever. A chest radiograph and spirometry will be performed at a follow-up visit. A panel of biomarkers related to endothelial activation, coagulation, and nitric oxide (NO) bioavailability will be obtained at several time points.
Sample Size: At least 56 subjects with SCD who are hospitalized for ACS.

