7.1.2 Description of Type of Study

This is a multi-center, randomized, double-blind, placebo-controlled Phase III clinical trial that will include at least 56 subjects with SCD who are hospitalized for ACS. Individuals who meet entry criteria will be randomized to receive either dexamethasone or placebo. Dexamethasone will be administered initially as 0.3 mg/kg by mouth every 12 hours for a maximum of 4 doses (2 days) or until discharge from the hospital, whichever occurs first. Afterward, the study drug will be tapered over 6 days for a total duration of therapy not to exceed 8 days. Due to possible age-related and ACS severity-related differences in the duration of signs and symptoms of ACS, randomization will be stratified by age and severity of ACS (see Section 8.3). We are enrolling a maximum of 112 pediatric subjects. We will enroll adult subjects at the rate site participation will allow, which we anticipate will be no more than 56 subjects. Interim analyses will be performed when a total of 56 subjects and 112 subjects have completed their hospital stay. If we do not stop enrollment after these interim analyses are completed, we will continue to enroll up to a maximum total of 112 pediatric subjects. The efficacy and safety of dexamethasone will be compared to placebo in the context of standard supportive care for ACS.

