1. The ACS Assessments are completed every 4 hours during hospitalization and at hospital discharge. The first 24 hour period begins at the time of the first dose of study drug on Day 0. i.e. First dose of study drug given on 05JAN07 @ 08:00, therefore Day 0 is from 05JAN07 08:00 – 06JAN07 07:59. The first Q 4 Hour ACS assessment begins as close as possible to 4 hours after first dose of study drug and the next routine nursing assessment. i.e. First dose given at 08:00, next routine nursing assessment is 13:00, therefore begin Q 4 Hour ACS assessments at 13:00 and time the following assessments from this time point. Even if an assessment is missed, this form should be completed and the appropriate expected time point should be selected.
2. Complete in the order the assessments are listed on the ACS Assessment worksheet.
3. Rate the respiratory rate and work of breathing **BEFORE** taking the oxygen off for one minute to check the O₂ saturation.
4. If subject is ventilated or if it is deemed unsafe to trial subject off O₂, then record “NA” (not applicable).
5. If steady state value is not known, enter 92%.
6. Enter a separate pain score for Thoracic and Non-thoracic pain with either the 10 point NRS or the Oucher (subjects 5 – 10 years).
7. **Invasive** ventilatory support means the use of an artificial airway (tracheal intubation) to support breathing. **Noninvasive** support means the use of positive pressure ventilation *without* the need for an invasive artificial airway, e.g. CPAP or BiPAP. The use of incentive spirometry or IPPV alone is **NOT** a form of noninvasive support.

Acute Chest Syndrome Assessment

Date of Assessment: _____

Time of Assessment: _____

Element of Index	Endpoint Criteria	Endpoint Met (Y/N)
1. Respiratory rate		
a. Current rate: _____	$a \leq b$	
b. Upper limit of normal ¹ (bpm) plus 2: _____		
2. Work of breathing		
a. Retractions (Y/N) _____	a = No	
b. Nasal flaring (Y/N) _____	b = No	
c. Use of accessory muscles (Y/N) _____	c = No	
3. Pain		
a. Thoracic pain scale ⁴ _____	$a \leq 4$	
b. Non-Thoracic pain scale _____		
4. S_pO₂ in room air²		
a. Current value: _____	$a \geq b$	
b. Steady-state value ³ (%) minus 2: _____		
5. Medical intervention		
a. Supplemental O ₂ (Y/N) _____	a = No	
b. Invasive or noninvasive ventilatory support (Y/N) _____	b = No	

¹Age 5-11.99 y, 30 bpm; age 12-17.99 y, 25 bpm; age ≥18 y, 20 bpm.

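### The mandatory blood-pressure adverse-event trigger is one 140/90 mmHg limit for everyone from age 5, so rises in children below it need not be reported as AEs and may miss the AE-based DSMB alerts

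*Protocol*

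**What the plan says.** Protocol Section 11.2.1 requires each site's principal investigator to review blood pressure at enrolment, daily in hospital and at both follow-up visits, and names three results that must be reported as AEs:

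- "A single blood pressure in which the systolic pressure is" at least 140 mmHg while the diastolic pressure is at least 90 mmHg;
- systolic at least 140 mmHg "on 2 more occasions in a rolling 24 hour period regardless of diastolic pressure";
- diastolic at least 90 mmHg "on 2 more occasions in a rolling 24 hour period regardless of systolic pressure".

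No age band is attached to any of them. The synopsis admits "Individuals of both genders 5 years of age and older". Section 7.1.2 says "We are enrolling a maximum of 112 pediatric subjects" and, of adults, "which we anticipate will be no more than 56 subjects".

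Other provisions that bear on the point:

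- **Risk.** Section 9.1.1 and the synopsis name hypertension as a possible dexamethasone effect. Sections 8.4 and 11.7 make new hypertension needing medication a discontinuation event, with no numeric limit.
- **Capture.** Blood pressure is recorded every 4 hours (Section 10.3.2), and study personnel collect the 24-hour maximum vital signs (Table 10.2, footnote 5).
- **Analysis.** Section 13.2.3 summarises vital signs by treatment, age stratum and time point. It tests AEs between arms only where they occur in more than 10% of subjects.
- **Alerts.** Sections 11.6.3 and 11.6.4 and Table 11.4 apply Fisher's exact test to counts of subjects with SAEs or AEs. The trend alert in Section 11.6.5 covers clinical laboratory data only.
- **Age bands elsewhere.** Appendix 3, footnote 1, sets the respiratory-rate limit at 30, 25 or 20 per minute by age.

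**The concern.** A fixed limit asks for a larger rise from a subject whose usual pressure is low than from one whose usual pressure is high. If young children's usual pressure is below that of adults, the rule is least sensitive in the group that makes up most of the planned sample.

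The formal safety signals run on AE counts. A rise that never becomes an AE adds nothing to the Fisher tests sent to the DSMB, and under-counting could keep hypertension below the 10% needed for the final chi-square comparison. The one alert that looks at shifts in measured values leaves blood pressure out. A pressor effect in children could therefore be visible in descriptive vital-sign tables yet trigger no alert.

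**Working it through.** The plan has no figure of its own to reproduce here. The check is how sensitive the trigger is at different usual pressures.

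**Inputs from the protocol:** limits of 140 and 90 mmHg (Section 11.2.1); readings every 4 hours, so 6 a day (Section 10.3.2); maxima of 112 children and 56 adults (Section 7.1.2).

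**Assumptions, since the protocol gives no values:** usual systolic pressure *m* of 100, 105, 110 or 120 mmHg; a sustained rise of 20 mmHg; reading-to-reading SD of 8 to 12 mmHg; independent, normally distributed readings in whole mmHg. The repeated-reading rule is taken to mean two or more readings.

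**Share of children at the maxima:** 112 / (112 + 56) = 67%.

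**Rise needed to reach 140:** 140 − *m*, which is 40, 35, 30 and 20 mmHg for *m* = 100, 105, 110 and 120.

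**Chance of meeting the repeated-systolic rule:**

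- One reading: p = 1 − Φ((139.5 − m − 20) / SD)
- At least two of six in a day: P1 = 1 − (1 − p)^6 − 6p(1 − p)^5
- On at least one of two days: P2 = 1 − (1 − P1)^2

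Example, *m* = 100 and SD = 12: z = 19.5 / 12 = 1.625, p = 0.052, P1 = 0.035, P2 = 0.07. Example, *m* = 120 and SD = 10: z = −0.05, p = 0.520, P1 = 0.908, P2 = 0.99.

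| Usual systolic (mmHg) | One day, SD 8 / 10 / 12 | One day, range | Two days, range |
|---|---|---|---|
| 100 | 0.001 / 0.009 / 0.035 | 0.1–3.5% | 0.2–7% |
| 105 | 0.017 / 0.066 / 0.142 | 2–14% | 3–26% |
| 110 | 0.150 / 0.274 / 0.380 | 15–38% | 28–62% |
| 120 | 0.912 / 0.908 / 0.905 | about 91% | about 99% |

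Two days is a fair horizon: mean stays on dexamethasone in the two earlier trials were 47 and 60 hours (Table 13.1).

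**Limits of the calculation.** It leaves out the diastolic rule and the single-reading rule, and it ignores pairs of readings that straddle two days under the rolling window. All of these would raise the chance of a report. The contrast between rows is more informative than any single row.

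**The case against.** Two stronger readings are tempting. One is that large rises in children go unrecorded; the other is that the trial could not detect this harm. The protocol supports neither.

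- Pressures are recorded every 4 hours, daily maxima are collected, and vital signs are tabulated by arm within age stratum.
- Section 11.2.1 sets a floor for reporting. Section 11.2 lets the investigator report any unfavourable sign as an AE, and the AE form invites comment: "The AE form will allow commentary about suspected causes of the hypertension (e.g., crying or severe pain").
- The discontinuation rule for new hypertension depends on the need for treatment and has no cut-off.
- Under Section 11.9.1 the DSMB receives a six-monthly report of all relevant safety information, so it is not confined to AE alerts.

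The comparison with respiratory rate also has limits. Those age bands define resolution of acute chest syndrome for the efficacy endpoint, so a different approach for AE reporting is not a contradiction. Section 9.1.1 links the listed steroid effects especially to chronic use, and treatment here lasts at most 8 days. The group under 18 includes adolescents, for whom the lowest assumed pressures may not apply.

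All of this stands, and it limits the point to mandatory reporting and alerting. It does not remove it. The vital-sign summaries carry no alert criterion, and discretionary reporting can differ between sites, which a mandatory list is meant to prevent.

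**Conclusion.** The point holds in a limited form. The mandatory trigger is not age-referenced, so rises in children below 140/90 need not be AEs and may not reach the AE comparison or the AE-based alerts. The measurements themselves are captured and summarised by age stratum.

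For the same 20 mmHg rise, the one-day chance of a mandatory systolic report runs from at most 3.5% at a usual 100 mmHg to about 91% at 120. Over two days it runs from at most about 7% to about 99%. The direction requires only that young children's usual pressures are lower than adults'. That is itself an assumption, as are the pressures, the SD and the size of the rise. The protocol does not allow an estimate of how many events would be missed in this trial. Severity is low to moderate: a cheap improvement to safety monitoring.

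**What to change.** 1. In Section 11.2.1, keep the present list for subjects aged 18 or over and make the mandatory trigger age-referenced for those under 18. The clinical team should set the values; none is proposed here.
2. In Section 11.6.5 and Table 11.4, extend the semi-annual trend alert to change from baseline in the daily maximum systolic and diastolic pressure, by arm and age group.

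The by-age summary of vital signs is already planned in Section 13.2.3 and needs no change. The cost is a protocol wording change, one more semi-annual analysis on data already collected, and more AE forms in children.

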11.3 Serious Adverse Events

A serious adverse event (SAE) is defined as any untoward medical occurrence that at any dose:

- Results in death;
- Is life-threatening (i.e., an event in which the subject was at risk of death at the time of the event; it does not refer to an event which hypothetically might have caused death if it were more severe).
- Requires inpatient hospitalization or prolongation of existing hospitalization.
- Results in persistent or significant disability/incapacity.
- Results in a congenital anomaly/birth defect.
- In the opinion of the investigator, important medical events that may not be immediately life-threatening or result in death or hospitalization but may jeopardize the subject or may require intervention to prevent one of the other outcomes listed in the definition above, may be considered serious. Examples of such events are intensive treatment in an emergency room or at home for allergic bronchospasm; blood dyscrasias or convulsions that do not result in hospitalization; or development of drug dependency or drug abuse.

11.4 Assessment of Adverse Event Severity and Relationship to Treatment

The following scale will be used to “grade” the severity of all AEs.

Table 11.1 Severity Scale for AEs

1	Mild. Awareness of sign, symptom, or event, but easily tolerated; does not interfere with usual daily activities or tasks.
2	Moderate. Discomfort enough to cause interference with usual daily activity; may warrant therapeutic intervention.
3	Severe. Incapacitating; inability to perform usual activities and daily tasks; significantly affects clinical status; requires therapeutic intervention.
4	Life-threatening. Adverse event is life-threatening.
5	Death. Adverse event causes death.

The standard nomenclature for defining the causal relationship between an AE and the study drug used by CSCC is listed in Table 11.2. The category that overall best “fits” the relationship between the AE and the study drug should be chosen and recorded on the CRF and SAE form, if necessary.

Table 11.2 Relationship Between Treatment and AE

Unrelated	
 • No temporal association to study product. • An alternate etiology has been established. • The event does not follow the known pattern of response to study product. • The event does not reappear or worsen with re-challenge.
Probably not related / remote	
 • No temporal association to study product. • Event could readily be produced by clinical state, environmental, or other interventions. • The event does not follow the known pattern of response to study product. • The event does not reappear or worsen with re-challenge.
Possibly related	
 • Reasonable temporal relationship to study product. • The event is not readily produced by clinical state, environmental, or other interventions. • The event follows a known pattern of response to the study product or as yet unknown pattern of response.

Probably related	
 • There is a reasonable temporal association with the study product. • The event is not readily produced by clinical state, environmental, or other interventions. • The event follows a known pattern of response to the study product. • The event decreases with de-challenge.
Definitely related	
 • There is a reasonable temporal relationship to the study product. • The event is not readily produced by clinical state, environmental, or other interventions. • The event follows a known pattern of response to the study product. • The event decreases with de-challenge and recurs with re-challenge.

Since all subjects enrolled in this study have sickle cell disease, it is anticipated that certain adverse events will occur related to the progression of the disease and this should be taken into account when determining whether or not an event is related to the therapy. Table 11.1 lists common sickle cell related events. Events on this list can still be related to therapy if the investigator determines that study drug may have triggered the event or made it more severe.

Table 11.3 List of Adverse Events Related to Sickle Cell Disease

Acne	Fluid Retention	Pain, long bone
Acute chest syndrome	Gastric Ulceration	Pain, severe abdominal
Anemia	Gastritis	Pancreatitis
Aplastic crisis	Glucosuria	Priapism
Aplastic crisis/anemia	Hand-foot syndrome	Psychoses
Arthralgia	Hematuria	Pulmonary thromboembolism (age \geq 18 yr only)
Avascular Necrosis	Hemiplegia	Pulmonary hypertension
Avascular necrosis of hip/shoulder	Hemolysis	Pulmonary parenchymal infiltrates on chest x-ray
Avascular necrosis of the femoral head	Hepatosplenomegaly	Pyelonephritis
Bone infarction	Hyperglycemia	Renal failure
Cardiomegaly	Hyperplastic bone marrow	Renal insufficiency/albuminuria
Cerebrovascular accident	Hypertension	Renal papillary necrosis
Cholecystitis, hepatic sequestration	Hyposthenuria	Reticulocytosis (\exists 10%–20%)
Cranial nerve palsy	Hypoxemia (PO ₂ < 65mm Hg)	Retinal disease
Decreased kidney function	Increased appetite	Retinal hemorrhage
Decreased lung function	Infection, pneumococcal	Rash
Delayed growth/puberty	Insomnia	Rhabdomyolysis
Delayed wound healing	Jaundice	Sepsis
Depressed ESR	Leukocytosis	Skin ulcers
Depression	Meningitis	Splenic sequestration
Dyspepsia	Mood Changes	Striae
Elevated urinary urobilinogen	Nausea and vomiting	Vaso-occlusive crisis
Fever	Pain, joint	Weight Gain
		Pulmonary parenchymal infiltrates on chest x-ray

An unexpected AE is an adverse reaction, the nature or severity of which is not consistent with the Dexamethasone label. Cases in which the AE is more severe than currently described in the Investigator's Brochure are also considered "unexpected."

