Randomization: Subjects in each of the two age groups (5-17 and ≥ 18 years of age) will be randomized to either the dexamethasone or placebo group (0.3 mg/kg every 12 hours x 4 doses, then tapered). Randomization will be stratified by site, age group, and severity of ACS to preserve balance across treatment groups.

Title of the Protocol: Randomized Trial of Oral Dexamethasone for Acute Chest Syndrome

Data Analyses: We will evaluate the difference in duration of symptoms for ACS between the two treatment groups using a generalized linear mixed model (GLMM). Here, the natural log of the duration of symptoms will act as the dependent variable of interest and the treatment status as the grouping factor. As a secondary analysis, the duration of hospitalization, supplemental oxygen, and fever will be analyzed in a similar manner. Laboratory parameters will be analyzed using a GLMM model, with treatment group, baseline laboratory value, age group, severity, and site as fixed effects and subject as a random effect. Clinical endpoints and AEs will be summarized by treatment and analyzed for differences across treatment group. Two formal interim analyses will be performed on the primary efficacy variable. The first interim analysis will take place when 56 subjects have resolved signs and symptoms of ACS OR have been discharged from the hospital. In this interim analysis, the primary efficacy hypothesis will be tested at the $\alpha = 0.001$ level. The study will be stopped if significant efficacy is identified. The second interim analysis will be performed when 112 subjects have resolved signs and symptoms of ACS OR have been discharged from the hospital. The primary efficacy hypothesis will be tested at the $\alpha = 0.01$ level. If significant efficacy is identified for total subjects and for children, the study will be stopped. Otherwise, the study will continue enrollment to 112 children, after which the primary efficacy hypothesis will be tested on the $\alpha = 0.039$ level.

Human Subjects: Potential risks include avascular necrosis, vaso-occlusive crisis, mood changes, hypertension, nausea, vomiting, dyspepsia, gastric ulceration, delayed wound healing, acne, and infection.

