9 TREATMENT OF SUBJECTS

9.1 Treatments

9.1.1 Description of Study Drug and Dosing Regimen

Dexamethasone is a commercially available synthetic corticosteroid hormone that is used primarily as an anti-inflammatory agent. It is available in tablets (several manufacturers), and as a solution for IV injection (several manufacturers).

Potential AEs, especially when given chronically, include hypertension, hyperphagia, weight gain, hyperglycemia, striae, acne, osteopenia, personality changes, gastrointestinal ulceration and hemorrhage, and growth retardation. Dexamethasone, like other steroids, may cause avascular necrosis of bone.

The dosing of dexamethasone, or an equivalent amount of placebo, is specified in Table 9.1. The initial dose (0.3 mg/kg every 12H) is given for a total of 2 days (4 doses) or until hospital discharge, whichever occurs first. Note: Time Zero is defined as the initial dose of study drug and the first 24 hour period begins with the first dose. All subsequent doses and study assessments are scheduled from this time point. Afterward, all subjects will receive the taper as specified in Table 9.1. All study drug should be given by mouth. If medications temporarily cannot be given by mouth (e.g. NPO status for a diagnostic test or altered mental status) then the temporary administration of the study drug by vein during this time period is acceptable. The dose of IV study drug is the same as the oral formulation. The study drug should be given by mouth as soon as oral medications can be tolerated.

Table 9.1 Dose and Frequency of Study Drug

Dose (mg/kg)	Max single Dose (mg)	Frequency	24hr dose (mg/kg)	Duration (days)	
0.3	12	Every 12H	0.6	2 (or hospital discharge)	} “High Dose”
0.3	12	Every 24H	0.3	2	
0.2	8	Every 24H	0.2	2	} “Taper”
0.1	4	Every 24H	0.1	2	

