13.2.3 Safety Analyses

Safety analyses will be performed on all randomized and dosed subjects (i.e., the ITT population). An analysis of safety will include a summary of AEs, SAEs, vital signs, clinical laboratory tests (CBC and reticulocyte count), physical examination, urine output and daily fluid balance, blood culture, peripheral oxygen saturation, and baseline and interim history. All safety outcomes will be summarized by treatment, age strata, and measurement time point (if appropriate).

Treatment-emergent AEs, drug-related AEs, SAEs, and drug-related SAEs (as determined by the investigator) will be classified using the Medical Dictionary for Regulatory Activities (MedDRA, Version 6.0 or later) preferred terms. A treatment-emergent AE is one that started or worsened in severity after initial administration of study drug. All treatment-emergent AEs and SAEs will be classified with regard to severity and duration of the event. These data will be summarized by treatment group, age strata, body system, and preferred terms within a body system. AE comparisons across treatment groups, stratifying on age group, will be made using a Chi-square test on any AEs that occur in more than 10% of the subjects. Each occurrence of an AE (classified on the basis of MedDRA terminology) will be reported separately for a given subject.

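### Table 11.3 labels most of the protocol's own named dexamethasone effects as sickle-cell events, which tilts causality ratings away from the drug

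*Protocol*

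**What the plan says.** Section 11.4 introduces a list with the statement that "it is anticipated that certain adverse events will occur related to the progression of the disease and this should be taken into account" in deciding whether an event is related to therapy. The list is Table 11.3, headed "List of Adverse Events Related to Sickle Cell Disease". The text cites it as Table 11.1, which is the severity scale. The next sentence allows that a listed event may still be related if the investigator thinks study drug triggered or worsened it.

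Two other places name drug or trial risks. The Synopsis, under Human Subjects, states: "Potential risks include avascular necrosis, vaso-occlusive crisis, mood changes, hypertension, nausea, vomiting, dyspepsia, gastric ulceration, delayed wound healing, acne, and infection". Section 9.1.1 gives as potential AEs of dexamethasone "hypertension, hyperphagia, weight gain, hyperglycemia, striae, acne, osteopenia, personality changes, gastrointestinal ulceration and hemorrhage, and growth retardation", and adds avascular necrosis in a separate sentence.

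Table 11.2 sets the causality criteria. *Possibly*, *probably* and *definitely related* each include the criterion that the clinical state or other interventions do not readily produce the event. *Probably not related / remote* includes the reverse: "Event could readily be produced by clinical state, environmental, or other interventions".

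Section 11.2 excludes from the AE definition the disorder being studied and its "expected progression, signs, or symptoms of the disease/disorder being studied unless more severe than expected" for the subject. Section 13.2.3 makes the investigator's rating a safety output: "drug-related AEs, SAEs, and drug-related SAEs (as determined by the investigator") are classified and summarized.

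**The concern.** The protocol attributes the same events to the drug in two places and to the disease in a third, and the third is the one investigators consult when they rate causality. Someone rating new hyperglycemia or acne is told that it is a common sickle-cell event, and must then decide whether the clinical state could readily have produced it.

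The output at stake is the summary of drug-related AEs and SAEs. Blinding means the tilt is not aimed at either arm. Genuine steroid effects, however, arise only in subjects who receive dexamethasone, so down-rating them lowers the drug-related count where it matters. Steroid toxicity is one of the reasons Section 5 gives for caution about this treatment.

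**Working it through.** No sample size, power or alpha is involved. The check is a term-by-term match of the two risk lists against Table 11.3, followed by a reading of Table 11.2.

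**Step 1: match the terms.** GI ulceration and GI hemorrhage are counted separately, and avascular necrosis is added to the 11 effects in the Section 9.1.1 list, giving 12.

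| Named effect | Synopsis | 9.1.1 | Entry in Table 11.3 |
|---|---|---|---|
| Avascular necrosis | yes | yes | yes (three entries) |
| Hypertension | yes | yes | yes |
| Acne | yes | yes | yes |
| Gastric / GI ulceration | yes | yes | Gastric Ulceration |
| Mood / personality changes | yes | yes | Mood Changes |
| Vaso-occlusive crisis | yes | – | yes |
| Nausea | yes | – | Nausea and vomiting |
| Vomiting | yes | – | Nausea and vomiting |
| Dyspepsia | yes | – | yes |
| Delayed wound healing | yes | – | yes |
| Infection | yes | – | only specific infections |
| Hyperphagia | – | yes | Increased appetite |
| Weight gain | – | yes | yes |
| Hyperglycemia | – | yes | yes |
| Striae | – | yes | yes |
| Growth retardation | – | yes | Delayed growth/puberty |
| Osteopenia | – | yes | no |
| GI hemorrhage | – | yes | no |

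**Step 2: count.**
- Synopsis: 10 of 11 (91%). The miss is infection in general; Table 11.3 has pneumococcal infection, sepsis, meningitis and pyelonephritis.
- Section 9.1.1: 10 of 12 (83%). The misses are osteopenia and GI hemorrhage.
- Both lists without duplicates: 11 + 12 − 5 shared = 18 effects, of which 15 match (83%).

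**Step 3: vary the matching.**
- Not accepting mood changes as a match for personality changes: Section 9.1.1 gives 9 of 12 (75%).
- Setting aside avascular necrosis, vaso-occlusive crisis and hypertension as plausible from either cause: 15 − 3 = 12 of 18 − 3 = 15 (80%).

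Most of the named effects are on the disease list in every variant.

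**Step 4: trace the effect on a rating.** Take new hyperglycemia on day 2 and accept the disease label in full. It meets two of the three *possibly related* criteria (timing and known pattern) and fails the clinical-state criterion. It meets one of the four *probably not related* criteria, the clinical-state one. Section 11.4 asks for the category with the best overall fit, which here is still *possibly related*. So the label removes one supporting criterion from every related category and adds one to *probably not related*. It shifts the balance without deciding the rating.

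**The case against.** The protocol contains real counterweights, and two stronger readings fail because of them.

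- **A reader might infer that a listed event falls automatically to *probably not related*.** The text does not support this. Ratings go by overall best fit, as step 4 shows, and Section 11.4 says listed events can still be related. No passage sets disease as the default cause.
- **A reader might infer that listed events go unrecorded and so drop out of the DSMB alerts.** That depends on stretching the Section 11.2 exclusion from the disorder being studied, which can be read as ACS alone, to everything in Table 11.3. Section 11.2 does not cite that table. It defines an AE regardless of relatedness and counts newly diagnosed conditions. Section 11.6.1 has all SAEs recorded. What stands is an ambiguity worth one clarifying sentence.

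The main safety comparisons also do not use attribution. Sections 11.6.3 and 11.6.4 test all recorded SAEs and AEs by arm, and Section 13.2.3 tests AEs seen in more than 10% of subjects. Expectedness is judged against the dexamethasone label and Investigator's Brochure, not Table 11.3. Defined blood pressure values must be reported as AEs, leukocyte counts come from the daily CBC, and rebound has its own quarterly test. All of this stands and limits the damage to the attributed summaries.

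The safeguard is coarse for uncommon events. Assuming 56 subjects per arm, the two-sided Fisher p-value for k events against none is 2 × C(56,k)/C(112,k): 0.0128 for k = 7 and 0.0060 for k = 8. Against the 0.01 threshold, seven affected subjects against none raises no alert, so smaller signals must be read from the tabulations, including the attributed ones.

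Finally, Section 9.1.1 qualifies its list as applying especially to chronic use, and the course here lasts at most 8 days. That bears on how often such events will occur, not on where they belong in the table.

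**Conclusion.** The point holds as an internal contradiction that pushes attribution in one direction. Of the 18 distinct effects the protocol names in its two risk lists, 15 also appear under a sickle-cell label that investigators are told to weigh. The exposed output is the investigator-judged drug-related AE and SAE summaries. How many ratings would change cannot be derived, because the protocol gives neither event rates for these terms nor a misattribution rate.

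The conclusion rests on three assumptions: that the Synopsis risks are meant as risks of the study drug, that the near-matches in the table above are fair (the count survives without the loosest one), and that investigators use Table 11.3 as Section 11.4 directs. It should be corrected, but it does not undermine the comparison of all recorded events between arms.

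**What to change.** 1. Remove from Table 11.3 the terms that the Synopsis or Section 9.1.1 names as risks or effects: acne, striae, weight gain, increased appetite, hyperglycemia, mood changes, gastric ulceration, dyspepsia, nausea and vomiting, delayed wound healing, and delayed growth/puberty.
2. Put terms plausible from both causes in a separate list flagged as possible effects of either disease or study drug: avascular necrosis (all three entries), vaso-occlusive crisis, hypertension and leukocytosis. Leukocytosis is in neither risk list, but Section 5 discusses it as both steroid-induced and part of ACS. The clinical team can add others.
3. State that every event on either list is recorded as an AE whatever its presumed cause, so that the Section 11.2 exclusion is not read to cover it.
4. Correct the reference in Section 11.4 from Table 11.1 to Table 11.3.

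Two further steps are not warranted: deleting terms that the two risk lists do not name (glucosuria, fluid retention, gastritis, insomnia, psychoses), and barring an *unrelated* rating.

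The cost is one table, a few sentences and a site memo. The downside is somewhat more AE forms and more events rated *possibly related*, in both blinded arms.
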